If the first documentation of CDA coincides with no disease activity (PDAI = 0), a follow-up visit  $\geq 2$  weeks later must still confirm that no new lesions are seen and PDAI = 0. At this time the patient is deemed to have confirmed CDA, ECP, and CR and therefore CS tapering can begin. If new lesion(s) are seen, the patient is no longer in CDA and therefore CS tapering should not begin. If a patient has not achieved CDA or new lesions emerge or existing lesions worsen but do not meet definition of relapse/flare, refer to Appendix 1 [Section 12.1](#) regarding increasing steroid dosage.

Throughout the Blinded Treatment Period, patients who fail to respond to treatment or experience a worsening of disease should have their CS dose increased per CS Management Guidelines (Appendix 1 [Section 12.1](#)) until CDA is obtained. If ECP is not achieved in a timely manner, it is encouraged that CS dose be further increased unless clinically contraindicated. The Principal Investigator (PI) should consult with the Medical Monitor in such cases.

Efficacy Outcome Assessment should be performed per the Efficacy Outcome Assessment Flowchart, Appendix 8 [Section 12.8](#).

Once patients achieve CR on a dose of 5 mg/day of CS, that dose should be maintained (not tapered further) until Study Week 37 (time of primary endpoint).

Rituximab treatment may be administered during the Blinded Treatment Period at or after the Week 5 Visit, only after a second “qualifying relapse/flare” occurs, unless contraindicated (Appendix 1 [Section 12.1](#)).

If rituximab is administered, patients should continue to take rilzabrutinib/placebo, remain on trial and blinded to treatment assignment. After completing the Blinded Treatment Period, patients will enter the Open-Label Extension Period to receive active treatment with rilzabrutinib described below. A patient in the Blinded Treatment Period requiring an additional “top up” dose of rituximab after their initial rituximab course of treatment must be discontinued from the trial.

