### 9.3.5 Efficacy analysis (mITT Population)

In general, the need for rituximab rescue will be considered “treatment failure” for the analysis of efficacy endpoints except cumulative CS and composite GTI score.

The analyses for efficacy endpoints involving clinical assessment of CR during the blinded treatment period will be performed based on data collected during on-site visits (i.e., not including data collected from remote visits) as the primary analyses.

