### Other analyses:

For analyses of following parameter,

- Change in PDAI score from baseline to Weeks 5, 13, 25, 37 and 61
- Total number of disease flares/relapses from initial CDA to Week 37
- Glucocorticoid Toxicity Index (GTI) score at Week 37
- Change in Autoimmune Bullous Disease Quality of Life (ABQOL) score from baseline to Weeks 5, 13, 25, 37, and 61

- Change in EuroQOL-5 Dimension 5 Level (EQ-5D-5L) results (visual analog scale [VAS] results and individual dimension) scores from Baseline to Weeks 5, 13, 25, 37 and 61.

If a patient receives a rituximab therapy, the study data up to the date of the first dose of rituximab (but not including data from the date of the first dose of rituximab) will be included in the analyses.

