	Cumulative duration of CR with a CS dose = 0 mg/day (days) from Baseline to Week 61	Zero-inflated negative binomial with terms for treatment group and disease history with an offset term based on the number of days on study during the Open-Label Extension Period
	GTI scores at Week 37	Analysis of covariance, with treatment, disease history as fixed effects, and baseline GTI score, baseline CS dose as covariates
	Change from Baseline in PDAI Score at Weeks 5, 13, 25, 37, and 61	MMRM with terms for treatment, week, baseline score, disease history, and treatment by week interaction
	Change from Baseline in ABQOL Score at Weeks 5, 13, 25, 37, and 61	MMRM with terms for treatment, week, baseline score, disease history, and treatment by week interaction
	Proportion of patients with ABQOL Score of zero at Weeks 5, 13, 25, 37, and 61	Cochran-Mantel-Haenszel test stratified by disease history at each visit
	Change from Baseline in EQ-5D-5L visual analog scale [VAS] results and individual dimension score categories at Weeks 5, 13, 25, 37 and 61	Continuous outcomes: MMRM with terms for treatment, week, baseline score, disease history, and treatment by week interaction. Categorical outcomes: Cochran-Mantel-Haenszel test stratified by disease history

	Endpoint	Analysis Method
	Time to first flare/relapse from initial CDA to Week 37	Log rank test stratified by disease history
	Time to first CR with a CS dose $\leq$ 10mg/day, from Baseline to Week 61	Log rank test stratified by disease history
	Proportion of patients with 3 or more lesions within 1 month or extension of established lesions that do not heal spontaneously within 1 week from Baseline to Week 37	Cochran-Mantel-Haenszel test stratified by disease history
	Total number of disease flares/relapses from initial CDA to Week 37	Zero-inflated negative binomial with terms for treatment group and disease history with an offset term based on the number of days on Post initial CDA

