### 8.3. Other Secondary Analyses

The following endpoints will be analyzed in a manner similar to that described for the primary endpoint in Section 8.1, with exception of the additional subgroup analyses described in Section 6.1.3.2:

- The proportion of patients who are in CR from Week 29 to Week 37 with a CS dose of  $\leq 5$  mg/day
- The proportion of patients who have a PDAI score  $< 3$  from Week 29 to Week 37 with CS  $\leq 10$  mg/day

Cumulative duration of CR with a CS dose  $\leq 10$  mg/day from Baseline to Week 61; cumulative duration of CR with a zero CS dose from Baseline to Week 61 and the cumulative duration of CR with a zero CS dose from Week 37 to Week 61 will be analyzed based on the same methods described for the cumulative duration of CR with CS dose  $\leq 10$ mg/day from Baseline to Week 37.

Change from baseline to Weeks 5, 13, 25, 37, and 61 in PDAI will be analyzed using restricted maximum likelihood (REML)-based mixed model for repeated measures (MMRM) with fixed effects for treatment, week, baseline PDAI and treatment by week interaction. For the analysis of the differences at Weeks 5, 13, 25, and 37, only all data up to Week 37 will be included in the model. For the analyses of the difference at 61 weeks, only data collected during the Open-Label Extension Period will be included in the model (from Week 39 onward). A contrast will be written within the MMRM model to get each Week-specific treatment difference (least squares treatment means, treatment difference estimates and 95% CIs). ABQOL and EQ-5D-5L overall VAS scores will be analyzed similarly.

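### The Week 61 MMRM uses open-label records only, so mITT patients who left or were first given rituximab in the blinded period drop out of the comparison, and baseline adjustment does not correct for selection on blinded-period disease activity

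*SAP*

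**What the plan says.** SAP 8.3 plans two separate mixed models for change in PDAI. For Weeks 5, 13, 25 and 37, "only all data up to Week 37 will be included in the model". For Week 61, "only data collected during the Open-Label Extension Period will be included in the model (from Week 39 onward". ABQOL and EQ-5D VAS are handled in the same way. The text gives "fixed effects for treatment, week, baseline PDAI and treatment by week interaction". Table 6 gives "MMRM with terms for treatment, week, baseline score, disease history, and treatment by week interaction", which adds disease history. Neither lists any blinded-period score as an outcome or covariate of the Week 61 model. Treatment differences with 95% CIs are to be reported.

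For patients given rituximab, SAP 6.1.5.2 uses "the study data up to the date of the first dose of rituximab" for these endpoints and excludes that date itself. The protocol (4.1, Blinded Treatment Period) keeps such patients in the trial: "If rituximab is administered, patients should continue to take rilzabrutinib/placebo, remain on trial and blinded to treatment assignment". They then enter the open-label period, so their later scores are collected but not used.

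SAP section 8 places all efficacy analyses in the mITT Population. Protocol 9.3.5 treats the need for rituximab rescue, in general, as treatment failure "for the analysis of efficacy endpoints except cumulative CS and composite GTI score". The protocol's own description of these mixed models (9.3.6, Other secondary) has no restriction to open-label data.

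**The concern.** A mixed model deals with drop-out by letting a leaver's earlier visits inform the later means. Restricting the Week 61 model to Week 39 onward removes those visits. A patient who left in the blinded period, or whose usable data stop there because of rituximab, then has no row at all.

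The protocol ties exit to disease activity after baseline. Under Appendix 1, a qualifying relapse needs a PDAI at or above the higher of the Screening and Day 1 scores, which means a change from baseline of at least zero on the analysed scale. Failure to reach disease control on corticosteroid is another route to rituximab. Severe, life-threatening disease is a listed reason for discontinuation (Protocol 7.2.1). Baseline adjustment does not remove selection of this kind.

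At stake is the reading of durability, a stated purpose of the open-label period. If more placebo patients are removed because of high PDAI, the remaining placebo patients are the more favourably selected group, and a lasting benefit of earlier treatment is understated.

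**Working it through.** The plan states no figure for this analysis, so there is none to reproduce. The check is in four steps.

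**1. Who has a row in the Week 61 model**

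- Withdrew before Week 39: no row.
- First rituximab dose in the blinded period: no row, because the data stop before Week 39.
- First rituximab dose in the open-label period: earlier open-label rows are kept.

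**2. Form of the bias**

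Let T be randomised arm, B baseline, Y1 a blinded-period score and Y61 the Week 61 score.

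- Model: E(Y61 | T, B, Y1) = a + h_T·T + h_B·B + h_1·Y1.
- True effect given baseline: h_T + h_1·g, where g is the coefficient of T in the regression of Y1 on T and B in all patients.
- Open-label-only estimate: h_T + h_1·g*, where g* is the same coefficient among those who remain.
- Bias: h_1·(g* − g).

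If exit depends only on B, g* = g. If it depends on Y1 but the arms do not differ in Y1, both are zero. If exit rises with Y1 and placebo has the higher Y1, g* lies closer to zero than g.

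**3. Size, by simulation**

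All inputs are assumptions:

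- SD 10; correlation of baseline with later visits 0.4; correlation between post-baseline visits 0.5 or 0.7.
- True Week 61 difference -3.0; blinded-period difference 0, -4 or -6.
- Exit or rescue logistic in blinded PDAI (slope 1.5 per SD), with overall rates of 10%, 20% and 30%.
- 20,000 per arm and six replicates, so that bias rather than sampling noise is seen.

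Each estimate cell shows correlation 0.5, then 0.7.

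| Overall exit | Blinded difference | Exit placebo / active | Full data | Open-label only | All visits |
|---|---|---|---|---|---|
| 10% | -4 | 12% / 8% | -3.07, -3.06 | -2.90, -2.81 | -3.06, -3.06 |
| 10% | -6 | 13% / 7% | -2.93, -3.10 | -2.67, -2.70 | -2.91, -3.10 |
| 20% | -4 | 23-24% / 16% | -2.99, -2.98 | -2.77, -2.60 | -3.03, -2.99 |
| 20% | -6 | 25% / 15% | -3.03, -3.07 | -2.61, -2.46 | -3.01, -3.05 |
| 30% | -4 | 35% / 25-26% | -3.00, -3.02 | -2.64, -2.52 | -2.95, -3.05 |
| 30% | -6 | 37% / 23% | -2.99, -3.01 | -2.48, -2.26 | -2.97, -3.04 |

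Open-label-only minus full data gives a bias toward zero of 0.17 to 0.40 points at 10% exit, 0.22 to 0.61 at 20% and 0.36 to 0.75 at 30%. The all-visit model stays within 0.05 of full data. With no blinded-period arm difference, or with exit driven by baseline PDAI alone, the open-label-only model is also within 0.05.

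The worst case agrees with step 2. There h_1 = (0.7 − 0.4²)/(1 − 0.4²) = 0.54/0.84 = 0.643. A bias of 0.75 means g* − g = 0.75/0.643 = 1.17, so the blinded difference among those remaining is about -4.8 rather than -6.

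**4. Size against sampling error**

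At 20% exit about 60 × 0.8 = 48 per arm remain. The standard error is roughly 10·√(1 − 0.4²)·√(2/48) = 9.17 × 0.204 = 1.87. The bias is then 0.22/1.87 = 0.12 to 0.61/1.87 = 0.33 standard errors. Coverage of a 95% CI at the upper value is Φ(1.63) − Φ(−2.29) ≈ 0.94.

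**The case against.** The strongest case for the plan is about the estimand. From Week 37 everyone takes rilzabrutinib, so Week 61 compares early with delayed start. An all-visit model describes what leavers would have scored had they stayed, avoided rituximab and, on placebo, switched to active drug. That assumes missing at random across a treatment switch. SAP 6.1.5.2 itself declines to infer a missing Week 37 relapse or new-lesion assessment from adjacent visits, because treatment before and after may differ. This stands as a reason to state the assumption. It does not rescue the open-label-only contrast, which is reported as a between-arm difference with a 95% CI in the mITT Population and needs the stronger assumption that exit is unrelated to blinded-period scores given the baseline terms.

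The limits on importance also stand. The endpoint is outside the hierarchy (SAP 6.1.4). The Weeks 5 to 37 comparison uses all data to Week 37. Disposition is tabulated by period and arm (SAP 7.1).

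A reader might infer more than the documents support:

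- That every patient given rituximab disappears. Those first treated in the open-label period keep their earlier open-label rows.
- That the model cannot handle drop-out at all. It adjusts for baseline score, and in Table 6 for disease history, so exit explained by these does no material harm.
- That a third to a half of an arm will be missing. No exit or rescue rate is given, rituximab is restricted to defined situations, and other worsening is met with corticosteroid increases while patients stay on study.

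SAP 6.1.5 promises imputation for secondary endpoints. No visible rule covers change in PDAI or quality of life after withdrawal, but 6.1.5.1 is partly redacted, so a rule cannot be wholly excluded.

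**Conclusion.** The point holds for selection driven by blinded-period disease activity. Patients who withdrew or were first given rituximab in the blinded period have no row in the Week 61 model, and nothing in that model carries their blinded-period scores. If such exit is commoner on placebo, the Week 61 difference shrinks toward zero by about 0.15 to 0.75 points on an assumed -3.0, for assumed overall exit of 10% to 30%. It is near zero if exit follows baseline only or the arms do not differ in the blinded period. Exit for other reasons could move the estimate the other way, and this was not modelled.

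At 60 per arm the bias is a fraction of a standard error, so it would rarely change a conclusion by itself. Under the mechanism described it hides benefit and does not create it. With the endpoint outside the hierarchy the priority is modest, but the repair is cheap enough to make.

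**What to change.** - In the mITT Population, fit one MMRM to all scheduled post-baseline visits at which each instrument is collected, using pre-rituximab data: PDAI at every visit from Week 3 to Week 61; ABQOL and EQ-5D VAS at Weeks 3, 5, 13, 25, 37, 39, 49 and 61. Include treatment, week, treatment-by-week, baseline score and disease history. Take the Week 61 contrast from it. This also settles the difference in model terms between the SAP 8.3 text and Table 6.
- State that the model assumes missing at random across the Week 37 switch to open-label drug.
- Name a fallback covariance structure. PDAI has 17 visits, so an unstructured matrix has 17 × 18/2 = 153 parameters in a trial of about 120 patients and may not converge. This is the small downside. The quality-of-life models, with 8 visits, need 8 × 9/2 = 36.
- Keep the open-label-only model, labelled as a description of patients in the open-label period.
- Report the number per arm contributing at Week 61.
- Reconcile the rituximab truncation in SAP 6.1.5.2 with the treatment-failure rule in Protocol 9.3.5.

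The cost is SAP wording and one changed model call, with no new data. It is best done before the Week 37 lock and unblinding described in SAP 4.3.

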#### 8.4. Exploratory Analyses

The number and percentage of patients with relapse after achievement of CR through Week 61 (Yes/No) will be presented by treatment group. A similar summary will be presented for patients that reached CR with a zero CS dose by from Week 53 to Week 61 (Yes/No).

Observed values and changes from Baseline in Treatment of Autoimmune Bullous Disease Quality of Life (TABQOL) will be presented at each study visit based on summary statistics by treatment group. Descriptive summaries for the Open-Label and Long Term Extension periods will report data by treatment group in double-blinded portion and overall.

The total number of disease flares/relapses from initial Week 37 to Week 61 will be analyzed based on the same methodology described for the cumulative duration of CR with CS dose  $\leq 10$ mg/day from Baseline to Week 37 in Section 8.2, using an offset term representing the time of patient participation in the Open-Label Treatment Period.

During the COVID-19 pandemic, measures to ensure continued drug supply and safety monitoring for patients were implemented. In-clinic study visits, as outlined in the protocol schedule of assessments, may be changed to a remote visit (e.g., telephone call, video call) as needed to address the COVID-19 restrictions. As a result, statistical analyses of efficacy endpoints involving CR assessment for the blinded treatment period will not include data collected from these remote visits. The incidence of remote visits and the corresponding reason for missing the onsite visits will be summarized by visit. Supportive analysis will be performed by including data collected remotely.

The analyses of the following endpoints will be documented and reported separately:

- Exploratory PK/PD analysis will examine the effects, if any, of covariates on PK and/or PD, and the relationship between PK, PD and efficacy in this population
- Cost utilities based on the number and type of hospitalizations, outpatient medical visits, concomitant medication use, adverse events and other relevant outcomes
- the temporal relationship of change in PDAI with changes in quality of life and health economic variables.

#### 9. Safety and Tolerability Analysis

Safety will be evaluated from reported TEAEs, changes in clinical laboratory values, changes in vital signs and physical exam results. All safety analyses will be performed on the Safety population. All summaries of safety will be presented for the blinded treatment portion of the study separately from the open-label portion of the study. The long term extension period will also be separately reported. All safety and tolerability data summaries will be reported by treatment group in double-blinded portion and overall. No statistical tests will be performed for any of the safety assessments.

## 9.1. Adverse Events

All AEs, TEAEs, and SAEs will be coded using the MedDRA dictionary version 24.0.

A TEAE is defined as any AE with an onset date/time on or after the first dose of study drug, having been absent pre-treatment or worsening relative to pre-treatment state. TEAEs will be broken down into Blinded Treatment Period TEAEs; Open-Label Extension Period TEAEs; and Long Term Extension TEAEs. A double-blind TEAE is defined as any TEAE with an onset date on or after the first dose of study drug and occurring before enrollment into the open-label portion of the study. TEAEs that are ongoing at the time of enrollment into the open-label portion are considered part of the double-blind portion of the study. An open-label TEAE is defined as any TEAE with an onset date on or after enrollment into the open-label portion of the study, having been absent during the double-blind portion or worsening relative to double-blind portion state. TEAEs for the long-term extension study will be determined similarly, based on the relative timing and severity of an event with respect to the end of the open-label period and start of the long term extension.

All summaries of TEAEs will be presented separately for the double-blind and open-label portions of the study for the Safety Population.

An overall summary of TEAEs will be presented including the total number of events, frequency counts, and percentages for:

- Any TEAEs
- Any treatment-related TEAEs
- Any TEAE leading to study discontinuation
- Any SAEs
- TEAEs resulting in death
- TEAEs by Grade (severity)
- Action Taken with Study Drug for all TEAEs (Study Drug Dose Not Changed, Study Drug Dose Interrupted, Study Drug Discontinued)
- TEAEs related to Corticosteroids

Summaries of the incidence of TEAEs and SAEs will be displayed by:

- SOC and PT
- SOC, PT, and maximum severity grade
- SOC, PT, and maximum causality (not related, related) to the study drug

In the case of multiple occurrences of the same TEAE within the same subject, each subject will only be counted once a preferred term. In the summaries showing severity and relationship to study medication the event with the maximum severity grade or strongest relationship (not related < related) will be reported. If an event is missing the severity, then severe will be used in the summary analyses (severity = severe); If an event is missing the relationship, then related

will be assumed for summary analyses (relationship = related). These data imputations are for categorization purpose only and will not be used in listings.

All TEAEs summarized by system organ class (SOC) and preferred term (PT) will be sorted in order of descending frequency of the SOC and then by descending frequency order (total across treatment groups) of the PT within each SOC.

In addition, summaries of TEAEs will be displayed by:

- SOC, HLGT, HLT and PT

In the AE data listings, all AEs will be displayed. AEs that are not treatment-emergent will be flagged.

### **9.1.1. Adverse Events Related to Corticosteroid Use**

A summary of incidence rates (frequencies and percentages) of TEAEs related to CS use, SOC, and preferred term will be prepared for the Safety Population.

### **9.1.2. Adverse Events Leading to Withdrawal**

A summary of incidence rates (frequencies and percentages) of TEAEs leading to withdrawal of study drug, by SOC, and preferred term will be prepared for the Safety Population.

A data listing of AEs leading to withdrawal of study drug will also be provided, displaying details of the event(s) captured on the CRF.

### **9.1.3. Deaths and Serious Adverse Events**

Any deaths that occur during the study will be listed.

Serious adverse events will be listed and also tabulated by system organ class and preferred term and presented.

## **9.2. Clinical Laboratory Evaluations**

Absolute values and changes from baseline will be summarized for clinical laboratory chemistry, hematology and coagulation results using descriptive statistics. The number of subjects with clinical laboratory values below, within, or above the normal range by time point will be tabulated for each clinical laboratory analyte. Shift tables for each clinical laboratory test will cross-tabulate the number of subjects with values below the laboratory reference range (low), values within the laboratory reference range (normal) or above the laboratory range (high) at baseline with the number of subjects with low, normal or high values at each post-baseline time point. Normal ranges and values outside the normal ranges will be identified by the central laboratory. A separate listing of out of normal range laboratory results will be provided.

A listing of all randomized subjects with pre-treatment and treatment-emergent laboratory values out of normal range will be presented.

Patients with positive urine pregnancy test results will be presented in by-subject listings.

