##### **8.6.3.6.1 Follow-up of abnormal laboratory test values**

In the event of unexplained clinically significant abnormal laboratory test values, the tests should be repeated as soon as possible and followed up until they have returned to the normal range and/or an adequate explanation of the abnormality is found. If a clear explanation is established, it should be recorded on the CRF.

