### 12.9.1 Appendix 9A - Remote Study Visits for Active Patients

#### Remote visit procedures to be performed:

1. Inform the patient that the study visit will be changed to a remote visit.
2. Obtain rilzabrutinib/placebo and corticosteroid amounts remaining with the patient. Based on the anticipated next in-clinic visit, determine whether the patient requires additional dispensing of rilzabrutinib/placebo and corticosteroids. If additional dispensing is needed, obtain details on date, time, and delivery address for the patient's home to confirm someone will be available to accept/sign for a home delivery. Follow options for IP transport instructions.
3. Email or mail Quality of Life (QOL) questionnaires to patients. The patient should keep them and provide the completed questionnaires when they return to the clinic, or the site can send a pre-printed and labeled Airway Bill to return via courier. The questionnaires include:
  - a. Autoimmune Bullous Disease Quality of Life (ABQOL) questionnaire
  - b. Treatment Autoimmune Bullous Disease Quality of Life (TABQOL) questionnaire
  - c. EuroQOL-5 Dimension 5 Level (EQ-5D-5L)
4. Where possible schedule a local lab visit. If a local lab is not available, please notify your local study monitor.
5. Collect the following critical study data via the phone call or video call. Document the conversation of the items below:
  - a. At a minimum, the following assessments must be performed by phone call:
    - i. New or changes in adverse events/serious adverse events
    - ii. New or changes in concomitant medications
    - iii. New or changes in Pemphigus concomitant medications
    - iv. Confirm IP compliance (corticosteroids and rilzabrutinib/placebo)
    - v. Confirm if changes in corticosteroid dosages are needed
  - b. If feasible and allowable per local regulations the following assessments should be performed:
    - i. PDAI assessment (must be done using video or photography for Investigator to visually review and confirm lesions)
    - ii. Disease efficacy outcome assessment (ie, CDA, ECP, CR, or Relapse/flare ; must be done using video or photography for Investigator to visually review and confirm lesions)
    - iii. Local labs performed (performed, yes/no, result and units)
    - iv. Home monitoring of vital signs (eg, weight and blood pressure)

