**6.1.6. Analysis Visit Windows**

For all analyses presented by study week, unscheduled and/or repeated measurements will only be included if a scheduled measurement is not available and the unscheduled/repeated measurement falls within the analysis visit windows as described below (Table 2 and Table 3). Otherwise, visits will be analyzed as scheduled.

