**Table 2: Analysis Visit Windows – Blinded Treatment Period**

Analysis Visit Name	Target Day of Planned Visit	Assessment Window (Days)
Week 3	15	Post-dose – Day 21
Week 5	29	22 – 42
Week 9	57	43 – 70
Week 13	85	71 – 98
Week 17	113	99 – 126
Week 21	141	127 – 154
Week 25	169	155 – 182
Week 29	197	183 – 210
Week 33	225	211 – 238
Week 37	253	239 – Pre-open label dose

If more than 1 visit occurs within a single visit window, then the analysis will use the visit closest to the target day. If 2 visits within the same visit window are equidistant from the target day, then the analysis will use the later visit.

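### The laboratory tables have no worst-value summary, so an abnormal unscheduled result is left out of every laboratory count by arm when a normal scheduled result exists in the same visit window

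*SAP*

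**What the plan says.** SAP 9.2 plans three kinds of laboratory table: descriptive summaries of values and changes, counts against the normal range, and shift tables. The counts are per visit ("The number of subjects with clinical laboratory values below, within, or above the normal range by time point will be tabulated"). The shift tables cross baseline category "with the number of subjects with low, normal or high values at each post-baseline time point". No table gives the number of patients abnormal at any time, or the worst post-baseline value. Protocol 9.3.4 likewise speaks of summaries by treatment group and time point, plus a shift table whose layout it does not specify.

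SAP 6.1.6 decides which value represents a visit. Its scope is wide ("For all analyses presented by study week") and has no exception for safety data. Within that scope, "unscheduled and/or repeated measurements will only be included if a scheduled measurement is not available", and the draw must also fall inside the window. Under Table 2: "If more than 1 visit occurs within a single visit window, then the analysis will use the visit closest to the target day". A tie goes to the later visit. Severity plays no part.

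SAP 9.2 adds listings of out-of-range results. On flags it says: "Normal ranges and values outside the normal ranges will be identified by the central laboratory". Protocol Appendix 9A lets patients with remote visits use local laboratories and names what is recorded: "Local labs performed (performed, yes/no, result and units".

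**The concern.** Protocol 8.4.7 allows laboratory safety tests at unscheduled times when the investigator thinks them necessary. Such draws are often prompted by a clinical worry, so they carry more safety information than a routine draw. Under SAP 6.1.6 a routine normal value in the same window displaces them.

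A visit-by-visit layout has a second limit. The same patient can be abnormal at several visits, so the per-visit counts cannot be added up to give the number of patients ever abnormal in each arm. For a short-lived, symptom-free rise in, say, a liver enzyme, that is the count a safety reviewer wants, and no planned table supplies it. Compared with a count over all draws, the selection rule can only lower the number of patients counted as abnormal; it cannot raise it.

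**Working it through.** **1. The rule on a concrete case.** Week 9 has target Day 57 and window Days 43–70 (SAP Table 2). Suppose the scheduled chemistry on Day 57 is normal and an unscheduled draw on Day 65 is high. Both days lie in the window and a scheduled value exists, so the Day 65 value is excluded and the patient is tabulated as within range at Week 9. If the Week 13 draw (Day 85) is normal again, the patient is never counted as high in any laboratory table.

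**2. How much of the blinded period is exposed.** Scheduled draws are at Weeks 3, 5, 9, 13, 25 and 37 (protocol Table 2, footnote e; that footnote lists the coagulation visits, and coagulation shares its row with hematology and chemistry). Window lengths come from SAP Table 2, starting at Day 2 and capping Week 37 at its target day, 253.

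| Window | Days | Length | Scheduled draw |
|---|---|---|---|
| Week 3 | 2–21 | 20 | yes |
| Week 5 | 22–42 | 21 | yes |
| Week 9 | 43–70 | 28 | yes |
| Week 13 | 71–98 | 28 | yes |
| Weeks 17 and 21 | 99–154 | 56 | no |
| Week 25 | 155–182 | 28 | yes |
| Weeks 29 and 33 | 183–238 | 56 | no |
| Week 37 | 239–253 | 15 | yes |

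- With a scheduled draw: 20 + 21 + 28 + 28 + 28 + 15 = 140 days; 140/252 = 55.6%.
- Without: 56 + 56 = 112 days; 112/252 = 44.4%. Here one unscheduled value per window is kept.

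**3. Illustrative size.** The documents give no rate of unscheduled draws, so this is an assumption: each affected patient has one abnormal value, seen only at an unscheduled draw on a uniformly random day, and all scheduled draws were taken and normal. The expected number left out is n × 140/252: for n = 3, 6 and 12 patients, about 1.7, 3.3 and 6.7.

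**4. Dependence on how long the abnormality lasts.** Assume instead that onset is uniform over the period and that every abnormality gets an unscheduled draw at its midpoint.

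| Duration | Missed by scheduled draws and dropped by the rule | Missed by scheduled draws but kept |
|---|---|---|
| 7 days | about 40% | about 46% |
| 14 days | about 24% | about 47% |
| 28 days | essentially none | about half |

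The remainder are caught by a scheduled draw. The loss is confined to short-lived abnormalities. The assumption that every abnormality is sampled at its midpoint has no support in the documents, so these shares show the pattern only.

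**5. Draws with no assigned place.** Week 113 has target day 112 × 7 + 1 = 785. The last window in SAP Table 3 ends on Day 770, 15 days earlier. Early termination has no row in either window table. Laboratory draws are planned at both (protocol Table 4, footnote c).

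**The case against.** The strongest answer is that the abnormalities that matter are counted elsewhere. Protocol 8.6.3.6 requires a treatment-emergent abnormal result to be recorded as an adverse event if it is symptomatic, changes study drug (including permanent discontinuation) or changes concomitant therapy. Protocol 8.6.3.2 adds abnormalities that need specific intervention or follow-up. SAP 9.1 tabulates these events by arm, and 9.1.2 has a separate table for events leading to withdrawal of study drug. Neither depends on visit windows. This stands, and it rules out a tempting inference that abnormalities leading to discontinuation are the ones most lost. It does not cover everything: protocol 8.6.3.2 leaves it to the investigator whether an isolated out-of-range result is an event at all, and a listing gives no counts by arm.

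Repeats are a weaker example than they look. Protocol 8.6.3.6.1 says that, for unexplained clinically significant abnormal values, "the tests should be repeated as soon as possible and followed up until they have returned to the normal range". If the first value was the scheduled one, SAP 6.1.6 keeps that abnormal value and drops the repeat, so the category is preserved.

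A reader might also infer that early-termination draws are lost. SAP 6.1.6 does not say so: they might be placed in a window or shown as their own visit. Nor does the SAP exclude local results. It names only the central laboratory as the source of flags and gives no rule for local ranges, while the case report form and data management plan, which might settle this, are not among the documents. The exclusion of remote-visit data in SAP 8 concerns complete-remission endpoints only.

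Finally, the rule applies alike to both arms and no safety tests are planned. No bias between arms is shown; the defect is an undercount.

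**Conclusion.** The point holds in a limited form. As written, the SAP leaves out of every laboratory count by arm an abnormal value seen only at an unscheduled draw in a window with a normal scheduled draw. Such windows cover about 56% of blinded-period days, and the loss falls on abnormalities short enough to pass between scheduled draws. The number of patients affected is unknown, because it depends on the frequency and timing of unscheduled draws.

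It would be wrong to read this as saying that unscheduled peaks drop out in general. Those in the Week 17, 21, 29 and 33 windows are kept, one per window, as is an unscheduled value that stands in for a missed scheduled one. The handling of early-termination, Week 113 and local-laboratory results is unstated, which is a gap in the text and not a demonstrated loss. With clinically significant abnormalities already counted as adverse events, the severity is modest.

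**What to change.** In SAP 9.2 add, per analyte, arm and study period, a shift from baseline category to the worst on-treatment value, once for the lowest and once for the highest, using all draws: scheduled, unscheduled, repeat and early termination. State in SAP 6.1.6 that the one-value-per-window rule applies only to by-visit summaries.

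Two clarifications should go with it. Say how early-termination and Week 113 draws are assigned to a visit or period. Say how local-laboratory results are classified against local reference limits.

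The cost is some SAP wording and one extra table per analyte. Reported abnormality counts will be higher, as expected when all draws are used. The main change needs no protocol amendment. Collecting local limits through Appendix 9A would need one, and protocol 10.2 requires ethics committee approval for all amendments; if the data collection already captures those limits, a sentence in the SAP is enough.
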